	
intake will be allowed for 60 minutes after taking medication or placebo. For subjects randomized to active treatment, their tablets will be 25 mg of ENT-01 each. Subjects randomized to active treatment with a baseline weekly CSBM rate of 0-0.9 will begin at 150 mg of ENT-01 and subjects randomized to active treatment with a baseline weekly CSBM rate of 1.0-3.0 will begin at 75 mg of ENT-01. Subjects randomized to placebo with a baseline weekly CSBM rate of 0-0.9 will begin at 6 placebo tablets and subjects randomized to placebo with a baseline weekly CSBM rate of 1.0-3.0 will begin at 3 placebo tablets.

Study Endpoints	
Primary Endpoints:
 
Primary Safety Endpoints:
 
Adverse events as evaluated with subject self-reporting, vital signs, clinical chemistry and hematology analyses on blood samples, urinalysis, and electrocardiograms (ECG).
 
Primary Tolerability Endpoints:
 
 • Recurrent vomiting. • Recurrent diarrhea. • Abdominal pain. • Dizziness. 
Primary Efficacy Endpoint:
 
Change from baseline in the weekly CSBM rate during the Fixed Dose period.
 
Secondary Efficacy Endpoints:
 
 • Frequency of dose adjustments in the Dose Adjustment period. • Prokinetic bowel response during the Fixed Dose period. • Change from baseline in the weekly SBM rate during the Fixed Dose period. • SBM bowel response to ENT-01 during the Fixed Dose period. • Change from baseline in stool ease of passage during the Fixed Dose period. • Change from baseline in stool consistency during the Fixed Dose period. • Change from baseline in suppository/enema use during the Fixed Dose period. • Time to first CSBM in the Fixed Dose period. • Time to first SBM in the Fixed Dose period. • Time to first rescue medication use in the Fixed Dose period. • Stool-related subjective assessments using the PAC-SYM and PAC-QOL. 
Exploratory Efficacy Endpoints:

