d. Sites will use a centralized computer-based system (IWRS) to obtain the randomization bottle(s) assigned to each subject.

- Subjects with baseline CSBMs from 0 to 0.9 will be randomized to begin treatment with ENT-01 150 mg or 6 tablets of placebo.
- Subjects with baseline CSBMs from 1.0 to 3.0 will be randomized to begin treatment with ENT-01 75 mg or 3 tablets of placebo.
- Subjects will self-administer study medication at home. The dose will be taken upon awakening, on an empty stomach with 8 oz. of water and no solid food will be taken for another 60 minutes. Subjects will remain in a sitting upright or standing position for at least 60 minutes after taking medication.
- Subjects will be advised to stay at home for 4 to 6 hours after taking the first dose of medication in case there is a need to evacuate urgently. After the first dose, subjects will know if and when to leave the house.

e. A subset of 20 subjects from this study population will participate in an L-Dopa PK Study, as follows:

- Visits 2 and 6: Blood draws for L-dopa levels (PK) will be drawn at Time zero.
- The first daily dose of L-Dopa will be administered on site after the first blood draw. There will be another blood draw at 20, 40, and 60 minutes post- L-Dopa dose.
- Visits 3, 4, and 5: Immediately upon arrival at the study site, the subject will take study medication (ENT-01 or placebo) on an empty stomach. Blood will be drawn at Time zero. 30 to 60 minutes after taking ENT-01 or placebo, the subject will take their first daily dose of L-Dopa. Blood will be drawn again 20, 40, and 60 minutes post-L-Dopa dose. The subject may have food 60 minutes after taking ENT-01.

f. Rescue medications will be dispensed as needed and instructions given concerning laxatives and other medications to treat constipation.

g. Subjects will be educated concerning use of the electronic diary to report stools immediately after a bowel movement.

CONFIDENTIAL

19April21_7.0

- h. The first 3 parts of the MDS-UPDRS should be administered while the subject is in an ON state, approximately one hour after taking L-Dopa (if applicable). In some cases, subjects will reach the "on" state earlier or later than at 60 minutes. In those cases, MDS-UPDRS should be performed when the Subject is "on".
- i. Those subjects who have a SAPS-PD score >0 on Visits 1 and 2 will have the SAPS-PD and hallucination/delusion questionnaire at all subsequent visits.

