The results of the study indicated that orally administered ENT-01 was safe and significantly improved bowel function and neurologic symptoms. Minimal systemic absorption suggests that improvements result from local stimulation of the ENS. Data from this study informed the development of the 2b study.

Phase 2b (ENT-01-030) Dosing Rationale

Dosing will range from 75 mg to 250 mg. The dose will be taken upon awakening on an empty stomach along with 8 oz. of water simultaneously to levodopa (if applicable). The compound is highly charged and will absorb to foodstuffs, so subjects will not be allowed to ingest any food for at least 60 minutes after taking study medication.

Subjects are not allowed to miss a dose, however, in the event this does happen, subjects must wait a minimum of 5 hours post ingestion of a meal and at least 1 hour prior to the next meal to take the missed dose.

In the recently completed Phase 2a study involving subjects with Parkinson's Disease-related constipation, ENT-01 was administered orally both in single-dose (Stage 1: n=10) and multiple daily doses (Stage 2: n=34) and was well tolerated to doses up to 250 mg. Maximal treatment duration in Stage 2 was 25 days. In this 2b study, daily doses of ENT-01 will be administered orally to subjects with Parkinson's Disease-related constipation and maximum treatment duration will also be 25 days.

Humans have long been exposed to low doses of squalamine (milligram to microgram) in the various commercial dogfish shark liver extracts available as nutraceuticals (e.g., Squalamax). In addition, following systemic administration squalamine is cleared by the liver and excreted as the intact molecule (in mice) into the duodenum through the biliary tract. Drug related GI toxicology has not been reported in published clinical trials involving systemic administration of squalamine. ENT-01 has limited bioavailability in rats and dogs. Based on measurement of portal blood concentrations following oral dosing of radioactive ENT-01 to rat's absorption of ENT-01 from the intestine is low. As a consequence, the principal focus of safety is on local effects on the gastrointestinal tract. However, ENT-01 appears to be well tolerated in both rats and dogs.

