- Improvement in cognition as assessed by the MMSE: The MMSE is an 11-item examination with a score ranging from 0 – 30 with a higher score indicating better memory. The MMSE will be summarized over time.
- Change in plasma L-Dopa levels 20, 40, and 60 minutes after L-Dopa and ENT-01 dose: An increase of >30% in peak plasma level during treatment versus baseline would indicate clinically significant increase in absorption attributable to ENT-01 (20 subjects).
- Change in stool microbiome during treatment: Since ENT-01 has antimicrobial properties in vitro, it may alter the intestinal microbiome; the subject's stool will be analyzed for common intestinal bacteria and viruses at Baseline and Fixed Dose, periods (20 subjects). If subjects discontinue from the study prior to the end of the Fixed Dose period, stool will be collected and analyzed at the Early Termination visit, as applicable.

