5.7 Concomitant and Prohibited Medication

- Preventive laxatives will be discontinued during the screening period. This will include all prescription laxatives, over the counter laxatives and dietary supplements. Throughout the study, subjects will be allowed to take constipation rescue medication on demand, and only if they have not had a bowel movement in three consecutive days. Rescue medications will be recorded in the electronic daily diary every time a laxative is used. Bowel movement produced within 24 hours of rescue medication or accidental self-prescribed laxative use will not be counted as either spontaneous bowel movement or complete spontaneous bowel movement.
- Proton pump inhibitors and antacids will be discontinued at the end of the screening period and reinstated during the wash-out period.
- Barbiturates, and opiates will be discontinued at the end of the screening period and 2-3 days before dosing and reinstated during the wash-out period. All medications shall be reviewed and dis/approved by the investigator on a case-by-case basis.
- Selective serotonin reuptake inhibitor (SSRI), SNRI, tricyclic antidepressant, anti-cholinergic, anti-histaminergic and anti-psychotic agents are permissible at stable doses.
- Dopamine agonists and amantadine will be allowed if on a stable dose for at least 2 weeks preceding the study.
- Deep brain stimulation is allowed if present for more than 6 months and at stable stimulation parameters.

Subgroup Analyses

[figure not shown]
Subjects will be analyzed overall by their randomized treatment assignment (i.e., active versus placebo). Subgroup analyses will also be performed by a subject's baseline CSBM rate (i.e., 0-0.9, or 1.0-3.0). The primary efficacy endpoint and key secondary, exploratory and safety endpoints will be summarized by these subgroups. Additional subgroup analyses may be defined in the statistical analysis plan (SAP).

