- Improvement in sleep as assessed by sleep diaries.
- Change in plasma L-Dopa levels 20, 40, and 60 minutes after L-Dopa and ENT-01 dose: An increase of >30% in peak plasma level during treatment versus baseline would indicate clinically significant increase in absorption attributable to ENT-01 (10 subjects only).
- Change in stool microbiome during treatment: Since ENT-01 has antimicrobial properties in vitro, it may alter the intestinal microbiome; the subject's stool will be analyzed for common intestinal bacteria and viruses at Baseline, Fixed Dose, and Washout periods (10 subjects only).

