4.2. General Statistical Methods and Data Handling

General Methods

All outputs will be incorporated into Microsoft Excel or Word files, sorted and labeled according to the International Conference on Harmonisation (ICH) recommendations, and formatted to the appropriate page size(s).

Tabulations will be produced for appropriate demographic, baseline, efficacy, pharmacokinetic and safety parameters. For categorical variables, summary tabulations of the frequency and percentage within each category (with a category for missing data) of the parameter will be presented. For continuous variables, the mean, median, SD, minimum and maximum values will be presented. Time to event data will be summarized using Kaplan-Meier Methodology using 25th, 50th (median), and 75th percentiles with associated 2-sided 95% confidence intervals, as well as percent of observed event rate and summary statistics for the follow-up time.

Formal statistical hypothesis testing will be performed on the efficacy endpoints with all tests conducted at the 2-sided 0.05 level of significance. Summary statistics will be presented, as well as confidence intervals on selected parameters, as described in the sections below.

For all analyses, baseline will be defined as the most recent measurement prior to the date and time of the administration of ENT-01 or placebo. Therefore, baseline may be on the same day as the dose of study treatment, but prior to the administration of the study treatment.

Computing Environment

All descriptive statistical analyses will be performed using SAS statistical software (Version 9.4), unless otherwise noted. Medical History and Adverse Events will be coding using the latest MedDRA version available upon the study start. Concomitant medications will be coded using the latest World Health Organization (WHO) Drug version available upon the study start.

Methods of Pooling Data

Not applicable to the present study.

Adjustments for Covariates

Statistical analyses for the efficacy endpoints will be adjusted by the randomization strata, the baseline CSBM rate (0 – 0.9 vs. 1.0 – 3.0).

Multiple Comparisons/Multiplicity

Adjustments for multiplicity will not be made for this study.

Subpopulations

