4.7. Pharmacokinetic Analysis

The plasma concentration data and PK parameters of L-Dopa will be summarized based on the PK population by time point (pre-dose, 20, 40 and 60 minutes post-dose) and dose level. These measures will be presented in listings as well.

An increase of $>30\%$ in peak plasma level of L-Dopa during treatment from baseline would indicate clinically significant increase in absorption attributable to ENT-01. The frequency and percentage of subject with clinically significant increase will be tabulated without formal statistical analysis for the PK population.

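### The exploratory L-Dopa rule credits ENT-01 with any within-subject rise of more than 30% over Visit 2: it contains no placebo contrast, and the written food conditions differ between the visits compared

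*Protocol*

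**What the plan says.** Protocol 3.3 sets the rule: "An increase of >30% in peak plasma level during treatment versus baseline would indicate clinically significant increase in absorption attributable to ENT-01". SAP 2.6.3 and SAP 4.7 repeat it. SAP 4.7 adds that the number and percentage of subjects meeting it "will be tabulated without formal statistical analysis for the PK population". SAP 3.1 defines that population as subjects with at least one L-Dopa result, with no restriction to the active arm.

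On baseline, SAP 4.2 states that "baseline will be defined as the most recent measurement prior to the date and time of the administration of ENT-01 or placebo".

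On visit conditions, footnote e (Protocol Table 1, Protocol Appendix 2 and SAP Table 1) provides for a time-zero draw, L-Dopa, then draws at 20, 40 and 60 minutes after L-Dopa. For Visits 2 and 6 it says nothing about food. For Visits 3, 4 and 5 it has the tablet taken on an empty stomach, L-Dopa 30 to 60 minutes later, and then: "The subject may have food 60 minutes after taking ENT-01". Protocol 4.3 and 4.4 ask sub-study subjects to arrive on an empty stomach and fix the gap at thirty minutes. The general rule in the synopsis, that no food "intake will be allowed for 60 minutes after taking medication or placebo", is tied to taking the study tablet.

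**The concern.** The rule turns a within-subject before-and-after change into a causal statement about the drug. Such a change also contains ordinary variation in a subject's peak from one visit to another, and any difference in the conditions of the two visits. Read literally, a placebo subject whose peak rises by more than 30% shows increased absorption due to ENT-01, a drug that subject never received.

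The visits being compared are not described alike. Fasting is written for the on-treatment visits and not for the baseline visit, and food is permitted inside the sampling window at the on-treatment visits. If food matters for L-Dopa levels, the contrast carries that difference as well as any drug effect.

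At stake is a descriptive statement about an interaction between ENT-01 and levodopa, a drug many of these subjects take daily. The primary and secondary endpoints are not involved.

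**Working it through.** The documents give no power, error rate or expected count for this sub-study, so there is no stated figure to reproduce.

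**1. Which visits the rule compares.** Visit 2 is the only visit with L-Dopa draws before dosing starts (Protocol Table 1), so under SAP 4.2 it is the baseline. Dosing begins at home the next day (Protocol 4.2). Visits 3 and 4 are the on-treatment visits. By Visit 5 every subject has been on single-blind placebo.

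**2. Conditions side by side.**

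| | Visit 2 | Visits 3 and 4 |
|---|---|---|
| L-Dopa dose | First or morning dose, in clinic | First or morning dose, in clinic |
| Time-zero draw | Yes | Yes |
| Study tablet in clinic | No | Yes, before L-Dopa |
| Empty stomach stated | No | Yes |
| Food limit stated | None | 60 minutes after the tablet |

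No tablet is scheduled at Visit 2, so the general food rule does not reach those draws.

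**3. Timing of draws against food.** Draw time after the tablet = gap + 20, 40, 60 minutes. Food is allowed from 60 minutes. Count the draws later than 60.

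| Gap, tablet to L-Dopa (min) | Draws after tablet (min) | Food allowed after L-Dopa (min) | Draws after permitted food |
|---|---|---|---|
| 30 (visit text) | 50, 70, 90 | 60 − 30 = 30 | 2 of 3 |
| 40 | 60, 80, 100 | 60 − 40 = 20 | 2 of 3 |
| 41 | 61, 81, 101 | 60 − 41 = 19 | 3 of 3 |
| 60 (footnote e upper limit) | 80, 100, 120 | 60 − 60 = 0 | 3 of 3 |

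A site using thirty minutes satisfies both the visit text and the footnote, so 2 of 3 is the natural reading and 3 of 3 the upper end.

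If food were held to the last draw, the hold would be gap + 60 minutes after the tablet: 30 + 60 = 90 at the thirty-minute gap, which is 90 − 60 = 30 minutes longer than now. No post-dose draw would then follow permitted food.

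**4. What the rule can flag with no drug effect.** The flag is met when on-treatment peak / Visit 2 peak > 1.30. With an unchanged on-treatment peak, a Visit 2 peak lowered by more than 1 − 1/1.30 = 23.1%, for any reason, meets it.

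The documents give no within-subject variability, so this part rests on an assumption. Take peaks as log-normal with a within-subject CV of 10% to 50% and no drug or food effect. The SD of the log ratio is √(2 ln(1 + CV²)), and the chance of a flag at one visit is 1 − Φ(ln 1.30 / SD), with ln 1.30 = 0.262.

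- CV 10%: SD = 0.141, chance 3.1%, or 0.6 of 20 subjects.
- CV 30%: SD = 0.415, chance 26.4%, or 5.3 of 20.
- CV 50%: SD = 0.668, chance 34.7%, or 6.9 of 20.

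The range is wide because the CV is unknown. It does show that a raw count of flagged subjects is not, without a comparator, evidence about the drug.

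**The case against.** The strongest reply is that the safeguard already exists. The sub-study sits in a randomised, placebo-controlled trial, and placebo subjects go through Visits 2, 3 and 4 under the same instructions. Comparing the arms removes any shift they share. The subgroup paragraph in Protocol 5.7 says that subjects are analysed by randomised treatment, and SAP 4.7 summarises concentrations by dose level. This stands, and it is why the remedy is small. It does not change the attribution sentence, which is within-subject in all three places, or the SAP 4.7 count, for which no split by arm is stated.

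Second, SAP 2.6.4 refers sample collection to a lab manual and the PK analysis to a separate SAP. Neither is supplied, and either could contain a fasting instruction or a comparison by arm. This also stands. The finding concerns what the two documents print, and the attribution wording would need correcting in any case.

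Third, food is permitted, not scheduled, and nothing in the documents says that food alters L-Dopa levels. The one stated reason for the food rule (Protocol 2.2) concerns ENT-01 binding to food. That is correct, so no direction or amount of bias can be claimed.

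A reader might point to the last item of Protocol 4.2, which mentions a second dose the next morning, and infer a clinic tablet at Visit 2. The rest of 4.2 places the first dose at home the following day, and the schedule marks no in-clinic tablet at Visit 2.

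**Conclusion.** The concern holds as a minor point about an exploratory endpoint. The stated rule attributes a within-subject rise of more than 30% over Visit 2 to ENT-01 with no placebo contrast, over a population that includes placebo subjects. The compared visits differ in their written food conditions, and 2 of 3 post-dose draws at Visits 3 and 4 follow permitted food at the thirty-minute gap (3 of 3 above 40 minutes). The attribution problem needs no assumption about food. The food problem matters only if food affects L-Dopa levels, which the documents do not address.

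Four stronger readings are tempting but not supported.

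- A reader might infer that the result is biased towards finding an interaction, or away from it. Neither size nor direction can be derived from the documents.
- A reader might infer that the sub-study cannot assess the drug at all. The concurrent placebo arm allows it, if the result is read that way.
- A reader might take the simultaneous dosing of tablet and levodopa in Protocol 2.2 as a third, conflicting PK gap. That is general dosing text. The PK-visit instructions are thirty minutes and 30 to 60 minutes, which are compatible at thirty.
- A reader might extend the food problem to Visit 6 and Early Termination. The rule compares treatment visits with Visit 2, so those visits do not bear on it. For Early Termination, the schedule marks no in-clinic tablet although Protocol 4.7 describes one.

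The sub-study size (20 in Protocol 3.3 and footnote e, 10 in SAP 2.6.3) is a separate inconsistency. At either size, a contrast between arms would be descriptive, as SAP 4.7 already intends.

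**What to change.** In Protocol 3.3, SAP 2.6.3 and SAP 4.7, tabulate the more-than-30% count separately for ENT-01 and placebo. State that a rise is attributed to ENT-01 only on the contrast between arms, read descriptively. This takes one sentence in each place, needs no new data, is consistent with Protocol 5.7 and applies equally to samples already taken.

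For sub-study subjects, require fasting arrival at Visit 2, hold food at Visits 2, 3 and 4 until the draw 60 minutes after L-Dopa, and set the gap in all three copies of footnote e to the thirty minutes used in the visit text. First check the lab manual and the separate PK SAP, so that an existing instruction is not duplicated or contradicted.

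The cost is wording in footnote e and Protocol 4.2 to 4.4, about 30 minutes more fasting at Visits 3 and 4, and a new fast at Visit 2. Samples collected before the change keep the old conditions and should be flagged.

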2 INTRODUCTION

Constipation is a common problem worldwide, affecting 2% to 27% of the population, with most estimates varying from 12% to 20% (Bouras and Tangalos, 2009). The prevalence of constipation increases to 30%-40% among people aged >65 years and women are disproportionately affected. In North America, 63M people meet the Rome IV criteria for constipation and in the US alone, constipation is responsible for over 2M physician visits annually. Laxatives are prescribed to 2- 3M patients every year and furthermore, in most patients, the condition is chronic requiring life- long treatment (Bouras and Tangalos, 2009).

Constipation is much more common among patients with Parkinson's Disease (PD) than in the general population. There are 1M people suffering from Parkinson's Disease in the US, of which roughly 60%, or 600,000 suffer from chronic constipation and in most, the condition is chronic, severe and unresponsive to standard therapy (Ondo et al., 2012; Zangaglia et al., 2007). This represents an economic burden to the individual with Parkinson's Disease and to the healthcare system. According to the most recent Federal Supply Schedule (FSS; April 2016), the average 30- day reimbursed price for a basket of orally administered drugs for constipation is approximately \$260 or \$3120 per year. This represents about \$1.8B of prescription laxatives just for patients with Parkinson's Disease. Constipation not only constitutes a major economic burden, but it also significantly affects the quality of life of the individual with Parkinson's Disease, contributing to social isolation and depression. Furthermore, the severity of the symptoms correlates negatively with patient reported quality of life.

An effective prokinetic medication for individuals with Parkinson's Disease would be a useful addition to the currently available treatments for this disabling condition.

